2.6.3 Exploratory clinical outcomes

The primary clinical outcome will be a composite of all-cause mortality, MI, non-hemorrhagic stroke, peripheral arterial thrombosis, and symptomatic, objectively confirmed VTE (DVT and/or PE). These outcomes will be monitored from randomization and over the specified follow-up period and will also be analyzed as individual outcomes, with the addition of CV mortality. We will also collect data on the length of stay and on re-hospitalizations, as measures of resource utilization.

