2.8 Participant timeline

The study schedule is reported in Figure 3.

Randomization will occur three to five days after surgery and will be timed to allow starting the intervention as soon as possible after allocation. The study personnel will follow patients throughout their hospital stay assessing the participants and reviewing their medical records, ensuring trial orders are followed, and noting any outcome. The study personnel will contact the patients via telephone (or in person, if the patient will not be discharged) 30 and 90 days after randomization and will obtain documentation as appropriate.

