2.9 Sample size

For this study, we set the target of enrolling 100 patients as a pragmatic sample size. This will allow us to show a complete 90-day follow-up in 95% of participants with a 95% CI ranging from 89% to 98%. We also calculated possible sample sizes for the full-scale trial. **Table 2** reports the sample size for different scenarios. We used the rate of cardiovascular events reported in the HIP-ATTACK trial: 0.18 overall, 0.30 in the subgroup with myocardial injury. For the effect size, we used the one reported in the COMPASS study, adding a more conservative and a more optimistic estimate. This provides the rationale for only including people with myocardial injury.

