Recruitment rate	(n of participants recruited)/month/site	≥ 2/month	1-2/month	<1/month
Screening to enrollment ratio	(n of eligible participants)/(n enrolled)	NA	NA	NA
30 days FUP	(n of participants with complete follow-up	≥ 95%	95-85%	< 85%
90 days FUP	data)/(n of enrolled participants)	≥ 95%	95-85%	< 85%
Treatment adherence	(n of pills/syringes prescribed – n of pills/syringes administered*)/(n of pills/syringes prescribed)	≥ 85%	85-75%	< 75%

FUP: follow-up, NA: not applicable.

Table 2: effect size for the full-scale trial, for different event rates and effect sizes.

Control event rate	Effect size (HR)	Sample size			
	0.70	1215			
0.30	0.75	1826			
	0.80	2967			
	0.70	1409			
0.25	0.75	2115			
	0.80	3434			
	0.70	1860			
0.18	0.75	2789			
	0.80	4524			

Based on the composite outcome measured in the HIP-ATTACK study: all-cause mortality, non-fatal myocardial infarction, non-fatal stroke, and non-fatal congestive heart failure. 0.30 was the event rate in people with baseline troponin elevation, 0.18 was the event rate in unselected patients with a baseline troponin measurement.

HR: hazard ratio Power set at 0.80.

^{*}Based on hospital records for the inpatient period and on patient-reported for the period after discharge.

[figure not shown]
Figures

Figure 1: comparison of rivaroxaban 2.5 mg BID + ASA 100 mg OD with rivaroxaban 5 mg BID, data from the COMPASS trial

		COMPASS		oxaban			Odds ratio
Study	Yes	No	Yes	No			with 95% CI
CV death, stroke, or myocardial infarction	379	8,773	448	8,669		_	0.84 [0.73, 0.96]
CV death	160	8,992	195	8,922	_		0.81 [0.66, 1.01]
Death from any cause	313	8,839	366	8,751			0.85 [0.73, 0.99]
Venous thromboembolism	25	9,127	36	9,081 -			0.69 [0.41, 1.15
Major bleeding	288	8,864	255	8,862			— 1.13 [0.95, 1.34
Minor bleeding	838	8,314	741	8,376		-	1.14 [1.03, 1.26]
					1/2	1	

CI: confidence interval; CV: cardiovascular.

Figure 2: HIPSTER Pilot design

¹With low-molecular weight heparin (LMWH) or a direct oral anticoagulant (DOAC)

Figure created with BioRender.com, dice by Marie Van den Broeck from Noun Project

²ASA 75-100 mg once daily + Rivaroxaban 2.5 mg twice daily

Figure 3: study schedule.

	STUDY PERIOD						
		Enrolment Allocation ¹		Post-allocation			Close-out
TIMEPOINT**	PreOD -1 to POD3	POD 3-5		POD 3-5	POD 30	POD 90	t_x^2
ENROLMENT:							
Eligibility screen		Х					
Troponin measurement ³	X	X					
Informed consent		Х					
2 gr Tranexamic acid IV ⁴	X						
Allocation			Х				
INTERVENTIONS:							

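### Does the 0.30 control rate behind Table 2 need re-deriving because section 2.9 and the Table 2 footnote describe it differently, and neither matches this trial?

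*Protocol*

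**What the plan says.** Section 2.9 fixes the pilot at 100 patients on pragmatic grounds and then lists possible sizes for a later full-scale trial in Table 2. It takes cardiovascular event rates from HIP-ATTACK, "0.18 overall, 0.30 in the subgroup with myocardial injury", and concludes: "This provides the rationale for only including people with myocardial injury".

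The Table 2 footnote is more specific. The source composite is "all-cause mortality, non-fatal myocardial infarction, non-fatal stroke, and non-fatal congestive heart failure". On the populations it says "0.30 was the event rate in people with baseline troponin elevation" and "0.18 was the event rate in unselected patients with a baseline troponin measurement".

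The pilot's primary clinical outcome, under the exploratory heading 2.6.3, is a "composite of all-cause mortality, MI, non-hemorrhagic stroke, peripheral arterial thrombosis, and symptomatic, objectively confirmed VTE". On timing, "These outcomes will be monitored from randomization and over the specified follow-up period", and section 2.8 says "Randomization will occur three to five days after surgery". Section 2.3.1 admits myocardial injury short of MI, found on presentation or within three days after surgery.

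**The concern.** A reader of 2.9 could take 0.30 as the expected control rate for this trial's patients and outcome. By the footnote it belongs to a different composite, and to troponin raised at baseline only. Neither place gives a start point or time horizon for the rate, while this trial counts from randomization on postoperative day 3 to 5.

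The rate does some work in the protocol. The contrast of 0.30 with 0.18 is offered as the reason for the myocardial injury criterion, and the 0.30 rows give the smallest full-scale sample sizes. If 0.30 were too high for the patients and outcome eventually studied, a trial sized on those rows would have too few events.

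**Working it through.** **1. The descriptions side by side**

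| Feature | Section 2.9 | Table 2 footnote | This pilot |
|---|---|---|---|
| Outcome | cardiovascular events | death, MI, stroke, heart failure | death, MI, non-hemorrhagic stroke, peripheral arterial thrombosis, VTE (2.6.3) |
| Group at 0.30 | myocardial injury | raised baseline troponin | injury short of MI, at presentation or by day 3 (2.3.1) |
| Group at 0.18 | overall | unselected, baseline troponin measured | not applicable |
| Start and horizon | not given | not given | from randomization, day 3 to 5; follow-up to 90 days |

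The differences in outcome and group are real. A difference in start point is possible but not shown, because no start point is given for 0.30. The Synopsis treats myocardial injury and an elevated troponin as the same thing, so those two terms are compatible. What differs is the timing and the exclusion of MI. The footnote applies one composite to both rates, so the comparison of 0.30 with 0.18 is like with like.

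**2. What in the pilot depends on 0.30**

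The precision statement in 2.9 uses only n = 100. The Wilson 95% interval for 95/100 is 88.8% to 97.8%, which matches the stated 89% to 98%. The progression criteria in Table 1 concern recruitment, follow-up and adherence. No event rate enters either.

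**3. How far Table 2 moves**

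Table 2's own cells:

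| HR | rate 0.30 | rate 0.25 | rate 0.18 | 0.25 vs 0.30 | 0.25 vs 0.18 |
|---|---|---|---|---|---|
| 0.70 | 1215 | 1409 | 1860 | +16% | -24% |
| 0.75 | 1826 | 2115 | 2789 | +16% | -24% |
| 0.80 | 2967 | 3434 | 4524 | +16% | -24% |

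For example, 2115/1826 = 1.158 and 2115/2789 = 0.758. If the injury group's rate were 0.25 rather than 0.30, restricting entry would still cut the sample size by about a quarter.

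**4. Check against a standard formula**

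Assume two-sided alpha 0.05, power 0.80, 1:1 allocation and no dropout. The Schoenfeld formula at HR 0.75 gives

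events = 4 × (1.960 + 0.842)² / ln(0.75)² = 379.4.

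N is events divided by the mean risk, with treated risk 1 − (1 − p)^0.75.

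- p = 0.30: mean risk 0.2674, N = 1419 (Table 2: 1826, ratio 1.29)
- p = 0.25: mean risk 0.2220, N = 1709 (Table 2: 2115, ratio 1.24)
- p = 0.18: N = 2384 (Table 2: 2789, ratio 1.17)

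Table 2 is not reproduced. Its alpha, method and dropout allowance are not stated, so this does not show it to be wrong. Under the same simple formula, 1826 patients would have power 0.89 at a control rate of 0.30, 0.83 at 0.25 and 0.69 at 0.18. The surplus over the formula may be an allowance for dropout, so 0.83 should not be read as spare margin.

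**5. Can the documents show which way 0.30 is off?**

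- Section 1.1 gives 29.6% at 90 days with ischemic myocardial injury (35% of patients) and 14.6% without. That supports a rate near 0.30 in the injury group, but the composite is not named.
- If those two groups made up everyone, the overall rate would be 0.35 × 29.6 + 0.65 × 14.6 = 19.9%, not 18%. But patients with non-ischemic injury may belong to neither group, and the footnote already says that 0.18 has its own denominator.
- Section 1.1 gives 9.5% deaths and 5.5% MI, at most 15.0% together. About 3 of the 18 points would then be stroke or heart failure, against 1.1% VTE that 2.6.3 adds. This compares whole-trial figures with a subset. Stroke and peripheral arterial thrombosis rates are not given.

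None of these fixes a direction.

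**6. Could the pilot settle it?**

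A pooled 25/100 has a Wilson 95% interval of 0.175 to 0.343. At HR 0.75 this corresponds to a control rate of about 0.20 to 0.38, which covers both 0.25 and 0.30.

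**The case for a change.** The best case for acting is that these rates justify an entry criterion of this very pilot, so they are more than a forecast for later. The composite in 2.6.3 is the only one defined for these participants. Section 2.13 foresees carrying pilot data into the full-scale analysis, and the list of full-trial efficacy outcomes in 2.14.2 does not name heart failure. The 0.25 row has no stated source, so Table 2 cannot be read as a deliberate adjustment. Correcting the text would cost almost nothing.

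Part of this stands. Section 2.9 is looser than its own footnote, and the time horizon is missing. The rest is weaker. Section 2.13 makes the carry-over conditional on an unchanged design. The list in 2.14.2 serves safety reporting: it does not name MI or stroke either, and it includes hospitalization, which is outside the 2.6.3 composite. The full-scale primary outcome is therefore not fixed, and a mismatch with it cannot be established. The entry criterion rests on a contrast between two rates of the same composite, and section 1.1 supports that contrast separately with 29.6% against 14.6%.

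**Conclusion.** No change is called for. Section 2.9 paraphrases loosely what the Table 2 footnote states precisely, and 2.9 sends the reader to that table. The rates are source-trial figures used to sketch possible full-scale sizes; no row is selected and no power is claimed for this pilot.

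An assumed 5-point shortfall, 0.25 in place of 0.30, raises Table 2's sample size by about 16% at each hazard ratio. It leaves the injury-only design about 24% smaller than the unselected one. That rests on Table 2's own cells and on 0.18 remaining the unselected rate. The documents show neither the size nor the direction of any actual error.

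Re-deriving the rate for this population and outcome needs source-trial data and a settled full-scale endpoint, so it belongs to the later protocol. The pooled event percentages with confidence intervals already planned in 2.13 will be available then, although 100 patients cannot separate 0.25 from 0.30. Bringing 2.9 into line with the footnote would be harmless editing, but it would alter no number, criterion or decision in this pilot.
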